5.15 SARS-CoV-2 testing. Will the subjects be tested for the SARS-CoV-2 coronavirus?

If the only testing is to screen the subjects (question 2.8), you do not need to answer this question

	No
	Yes

→ If yes:

- Name the testing lab
- Confirm that the lab and its use of this test is CLIA-certified or certified by the Washington State Department of Health
- Describe whether you will return the results to the participants and, if yes, who will do it and how (including any information you would provide to subjects with positive test results).

5.16 Research equipment and COVID-19. Does your research involve any equipment that will be used on more than one subject that is not part of a clinical facility?

Examples: a computer tablet, a portable research ultra-sound device).

	No
	Yes

→ If yes: confirm by checking the box below that the disinfection and cleaning of the equipment will meet the enhanced UW Environmental Health & Safety requirements described here:
<https://www.ehs.washington.edu/system/files/resources/cleaning-disinfection-protocols-covid-19.pdf>

Confirmed

6 CHILDREN (MINORS) and PARENTAL PERMISSION

6.1 Involvement of minors. Does the research include minors (children)?

Minor or child means someone who has not yet attained the legal age for consent for the research procedures, as described in the applicable laws of the jurisdiction in which the research will be conducted. This may or may not be the same as the definition used by funding agencies such as the National Institutes of Health.

- In Washington State the generic age of consent is 18, meaning that anyone under the age of 18 is considered a child.
- There are some procedures for which the age of consent is much lower in Washington State.
- The generic age of consent may be different in other states, and in other countries.

No → If no, go to [Section 8](#).

Yes → If yes, provide the age range of the minor subjects for this study and the legal age for consent in the study population(s). If there is more than one answer, explain.

Age 13-16: Legal age in [REDACTED] is 18

All participants are treated as minors and we will obtain parental permission and student assent.

Don't know → This means is it not possible to know the age of the subjects. For example, this may be true for some research involving social media, the Internet, or a dataset that is obtained from another researcher or from a government agency. Go to [Section 8](#).

6.2 Parental permission. **Parental permission** means actively obtaining the permission of the parents. This is not the same as "passive" or "opt out" permission where it is assumed that parents are allowing their children to participate because they have been provided with information about the research and have not objected or returned a form indicating they don't want their children to participate.

a. Will parental permission be obtained for:

All of the research procedures → Go to [question 6.2b.](#)

None of the research procedures → Use the table below to provide justification, and skip question 6.2b.

Some of the research procedures → Use the table below to identify the procedures for which parental permission will not be obtained.

Be sure to consider all research procedures and plans, including screening, future contact, and sharing/banking of data and specimens for future work.

Children Group ¹	Describe the procedures or data/specimen collection (if any) for which there will be NO parental permission ²	Reason why parental permission will not be obtained	Will parents be informed about the research? ³	
			YES	NO
				
				
				

[figure not shown]

Table footnotes

1. If the answer is the same for all children groups or all procedures: collapse the answer across the groups and/or procedures.
2. If identifiable information or biospecimens will be obtained without parent permission, any waiver granted by the IRB does not override parents' refusal to provide broad consent (for example, through the Northwest Biotrust).
3. Will parents be informed about the research beforehand even though active permission is not being obtained?

b. Indicate the plan for obtaining parental permission. One or both boxes must be checked.

Both parents, unless one parent is deceased, unknown, incompetent, or not reasonably available; or when only one parent has legal responsibility for the care and custody of the child

One parent, even if the other parent is alive, known, competent, reasonably available, and shares legal responsibility for the care and custody of the child.

This is all that is required for minimal risk research.

If both boxes are checked, explain:

6.3 Children who are wards. Will any of the children be wards of the State or any other agency, institution, or entity?

X	No
	Yes

→ If yes, an advocate may need to be appointed for each child who is a ward. The advocate must be in addition to any other individual acting on behalf of the child as guardian or in loco parentis. The same individual can serve as advocate for all children who are wards.

Describe who will be the advocate(s). The description must address the following points:

- Background and experience
- Willingness to act in the best interests of the child for the duration of the research
- Independence of the research, research team, and any guardian organization

6.4 UW Office for Youth Programs Development and Support. If the project involves interaction (in-person or remotely) with individuals under the age of 18, researchers must comply with **UW Administrative Policy Statement 10.13** and the requirements listed at [this website](#). This includes activities that are deemed to be Not Research or Exempt. It does not apply to third-party led research (i.e., research conducted by a non-UW PI). [Information and FAQs](#) for researchers are available.

This point is advisory only; there is no need to provide a response.

7 ASSENT OF CHILDREN (MINORS)

Go to [Section 8](#) if your research does not involve children (minors).

7.1 Assent of children (minors). Though children do not have the legal capacity to “consent” to participate in research, they should be involved in the process if they are able to “assent” by having a study explained to them and/or by reading a simple form about the study, and then giving their verbal choice about whether they want to participate. They may also provide a written assent if they are older. See [WORKSHEET Children](#) for circumstances in which a child’s assent may be unnecessary or inappropriate.

a. Will assent be obtained for:

All research procedures and child groups

→ Go to [question 7.2.](#)

None of the research procedures and child groups

→ Use the table below to provide justification, then skip to [question 7.6](#)

Some of your research procedures and child groups

→ Use the table below to identify the procedures for which assent will not be obtained.

Be sure to consider all research procedures and plans, including screening, future contact, and sharing/banking of data and specimens for future work.

Children Group ¹	Describe the procedures or data/specimen collection (if any) for which assent will NOT be obtained	Reason why assent will not be obtained

Table footnotes

1. If the answer is the same for all children groups or all procedures, collapse your answer across the groups and/or procedures.

7.2 Assent process. Describe how assent will be obtained, for each child group. If the research involves children of different ages, answer separately for each group. If the children are non-English speakers, include a description of how their comprehension of the information will be evaluated.

For students whose parent/guardian indicated they have permission to take the class, they will be invited to attend a research orientation meeting during their onsite school orientation. Students arrive to the school two weeks before classes start to move into their dorms, settle in, learn about class topics for the year and school activities. A research orientation session will occur during the first week of their 2-week pre-school orientation period.

At the orientation meeting, a study package will be handed to each youth. The package will include Native items such as sage or lavender, a writing pad and pen and pencil with a Native design and study phone number, two copies of the assent form (one for them to sign and the other to keep as their copy), and the study flyer. UW and [REDACTED] staff will inform the students about the research project, highlighting that it is

completely voluntary and then review the assent form and ask for questions. At the end of the meeting, students will be instructed to write their names on the assent form and indicate if they are interested in participating in the project (Yes/No) or would like more information. Students who are interested in participating will also be asked to fill out a contact information sheet, which asks for their name(s), birth date, preferred pronouns, email address, phone number, and space to provide any additional contact information (ex., social media). If they would like more information, they will be asked to provide contact information (similar to that of those who have assented) and a UW staff person will contact them. They will be informed that they may also reach out to the UW or [REDACTED] staff at any time before the first day of class (within the two weeks) if they have any additional questions about participation.

Students will hand in one signed copy of the assent form when they exit the room.

UW or [REDACTED] staff will then follow-up with students that indicated they are interested in participating and welcome them to the program and asked if they have any additional questions. They will also follow-up with students who request additional information.

For students that have indicated they are interested, they will be randomly assigned to a class offering the intervention sessions. Some classes will start the intervention curriculum in the Fall, others in the Spring. Students that indicated they are not interested they will be assigned to a class that is not participating in the intervention curriculum. This is easily done as there are multiple classes for each grade.

Students may choose to drop out of the research program by notifying research staff by email and reassignment to a health class will be provided. As standard practice, students periodically change class assignments so this would not seem out of the norm.

7.3 Dissent or resistance. Describe how a child's objection or resistance to participation (including non-verbal indications) will be identified during the research, and what the response will be.

Turn in an assent form without a name or marked "no, not interested."

Over the course of the 6-month program, participants may decline further participation by sending an email to the study team email address. All communication and all documents will provide a reminder that participation is voluntary.

7.4 E-consent. Will any electronic processes (email, websites, electronic signatures, etc.) be used to present assent information to subjects/and or to obtain documentation (signatures) of assent? If yes, describe how this will be done.

no

7.5 Documentation of assent. Which of the following statements describes whether documentation of assent will be obtained?

None of the research procedures and child groups

→ Use the table below to provide justification, then go to [question 7.5.b](#)

All of the research procedures and child groups

→ Go to [question 7.5.a](#), do not complete the table

Some of the research procedures and/or child groups

→ Complete the table below and then to go
[question 7.5.a](#)

Children Group ¹	Describe the procedures or data/specimen collection (if any) for which assent will NOT be documented
-----------------------------	--

Table footnotes

1. If the answer is the same for all children groups or all procedures, collapse the answer across the groups and/or procedures.

a. Describe how assent will be documented. If the children are functionally illiterate or are not fluent in English, include a description of the documentation process for them.

All students attending the school in the 9th grade are literate and fluent in English. Documentation is their signature on the assent form.

b. Upload all assent materials (talking points, videos, forms, etc.) to **Zipline**. Assent materials are not required to provide all of the standard elements of adult consent; the information should be appropriate to the age, population, and research procedures. The documents should be in Word, if possible.

7.6 Children who reach the legal age of consent during participation in longitudinal research.

Children who were enrolled at a young age and continue for many years: It is best practice to re-obtain assent (or to obtain it for the first time, if it was not obtained at the beginning of their participation).

Children who reach the legal age of consent: Informed consent must be obtained from the now-adult subject for (1) any ongoing interactions or interventions with the subjects, or (2) the continued analysis of specimens or data for which the subject's identify is readily identifiable to the researcher, unless the IRB waives this requirement.

a. Describe the plans (if any) to re-obtain assent from children.

The week before the Spring semester, students in the second wave will be emailed a welcome reminder about their upcoming spring research class. The reminder will include the study email address, study phone number, a copy of an assent form, a reminder their participation is voluntary, and a reminder that if they have any questions to please contact staff at the contact information provided (study email and phone is monitored by the UW staff). On the first day of Spring class, UW and [REDACTED] staff will go to the study classes to review the assent forms, the study email address, study phone number, highlight that participation is voluntary, and ask students if they have any questions to please contact staff with the contact information provided.

b. Describe the plans (if any) to obtain consent for children who reach the legal age of consent.

- If adult consent will be obtained from them, describe what will happen regarding now-adult subjects who cannot be contacted.
- If consent will not be obtained or will not be possible: explain why.

Age range of children are 13-16. It will be impractical to obtain consent for continued data analysis when the minor participants turn 18.

7.7 Other regulatory requirements. (This is for information only; no answer or response is required.) Researchers are responsible for determining whether their research conducted in schools, with student records, or over the Internet comply with permission, consent, and inspection requirements of the following federal regulations:

- PPRA – Protection of Pupil Rights Amendment
- FERPA – Family Education Rights and Privacy Act
- COPPA – Children’s Online Privacy Protection Act

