Examples: inform subjects about other studies; ask subjects for additional information or medical record access that is not currently part of the study proposed in this application; obtain another sample.

5.13 Alternatives to participation. Are there any alternative procedures or treatments that might be advantageous to the subjects?

If there are no alternative procedures or treatments, select "No". Examples of advantageous alternatives: earning extra class credit in some time-equivalent way other than research participation; obtaining supportive care or a standard clinical treatment from a health care provider instead of participating in research with an experimental drug.

No
 Yes

→ If yes, describe the alternatives.

Any student not interested in the study will have the option to stay in the class, but will not be asked to complete surveys.

5.14 Upload to Zipline all data collection forms (if any) that will be directly used by or with the subjects, and any scripts/talking points that will be used to collect the data. Do not include data collection forms that will be used to abstract data from other sources (such as medical or academic records), or video recordings.

- **Examples:** survey, questionnaires, subject logs or diaries, focus group questions.
- **NOTE:** Sometimes the IRB can approve the general content of surveys and other data collection instruments rather than the specific form itself. This prevents the need to submit a modification request for future minor changes that do not add new topics or increase the sensitivity of the questions. To request this general approval, use the text box below to identify the questionnaires/surveys/ etc. for which you are seeking this more general approval. Then briefly describe the scope of the topics that will be covered and the most personal and sensitive questions. The HSD staff person who screens this application will let you know whether this is sufficient or whether you will need to provide more information.
- **For materials that cannot be uploaded:** upload screenshots or written descriptions that are sufficient to enable the IRB to understand the types of data that will be collected and the nature of the experience for the participant. You may also provide URLs (website addresses) or written descriptions below. Examples of materials that usually cannot be uploaded: mobile apps; computer-administered test; licensed and restricted standardized tests.

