10.6 Data and Safety Monitoring. A Data and Safety Monitoring Plan (DSMP) is required for clinical trials (as defined by NIH). If required for this research, or if there is a DSMP for the research regardless of whether it is required, upload the DSMP to **Zipline**. If it is embedded in another document being uploading (for example, a Study Protocol) use the text box below to name the document that has the DSMP. Alternatively, provide a description of the DSMP in the text box below.

Attached

10.7 Un-blinding. If this is a double-blinded or single-blinded study in which the participant and/or relevant study team members do not know the group to which the participant is assigned: describe the circumstances under which un-blinding would be necessary, and to whom the un-blinded information would be provided.

no

10.8 Withdrawal of participants. If applicable, describe the anticipated circumstances under which participants will be withdrawn from the research without their consent. Also, describe any procedures for orderly withdrawal of a participant, regardless of the reason, including whether it will involve partial withdrawal from procedures and any intervention but continued data collection or long-term follow-up.

n/a

10.9 Anticipated direct benefits to participants. If there are any direct research-related benefits that some or all individual participants are likely to experience from taking part in the research, describe them below:

Do not include benefits to society or others, and do not include subject payment (if any). Examples: medical benefits such as laboratory tests (if subjects receive the results); psychological resources made available to participants; training or education that is provided.

Participants may benefit by learning more about themselves through participation in the study, learning about how to make healthy behavioral changes, learning youth leadership skills and learning digital storytelling skills, or going on a field trip.

They may also feel good about helping an effort that is aimed at improving the health and wellness of Native American youth across the country.

10.10 Return of individual research results.

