Journey of Transformation Curriculum for Native American Adolescents (JOT)

NCT05274217

[name]

Statistical Analysis Plan

IRB Approved 03-16-2021

Statistical Design and Power

This study will evaluate the following primary outcomes: (1) alcohol, tobacco, and other drugs (ATOD; intentions to use, overall use, susceptibility, refusal self-efficacy) and (2) sexual and reproductive health (sexual activity, sexual self-efficacy, safer sex intentions). An intent-to-treat approach will be used to estimate the magnitude and statistical significance of intervention effects at immediate post-intervention. Each outcome will be evaluated in a separate generalized linear mixed model to evaluate the effect of CHJOT curriculum on intervention outcomes. Continuous outcomes will be modeled using a Gaussian link function for normally distributed data and binary outcomes using a logit link for Bernoulli-distributed data. The following equation represents the basic model for the outcomes: $Outcome_{tij} = b_0 + b_1 Intervention_i + b_2 Time + b_3 (Intervention_{ij} \times Time_{tij}) + u_{0i} + r_{0ij} + e_{tij}$, where t indexes assessment, i indexes individual, and j indexes classroom. The last three terms on the right side of the model equation represent the variability between classrooms (u_{0i}), between individuals within classroom (r_{0ij}), and residual error (e_{tij}), respectively. The statistical test of the CHJOT curriculum will be the Intervention by Time interaction, which will evaluate whether recipients of the intervention curriculum improved more or decreased less from pre- to 2-month post-intervention compared with waitlist control.

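### Only whole-study withdrawal is described, so outcomes of students who stop the curriculum may be missing from the promised intent-to-treat analysis

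*Protocol*

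**What the plan says.** **Leaving the study.** Protocol 7.2: "Students may choose to drop out of the research program by notifying research staff by email"; the same sentence then provides for a move to a health class. It adds that class changes are ordinary at this school. Protocol 7.3: "participants may decline further participation by sending an email to the study team email address". Neither section distinguishes stopping the curriculum from stopping the surveys.

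**Continued data collection.** Protocol 10.8 asks for the procedures for orderly withdrawal, whatever the reason, "including whether it will involve partial withdrawal from procedures and any intervention but continued data collection or long-term follow-up". The answer to the whole item is n/a.

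**Class and surveys apart.** Protocol 5.13 separates them in one direction: "Any student not interested in the study will have the option to stay in the class, but will not be asked to complete surveys". The reverse case, out of the class but still surveyed, is not described.

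**Analysis.** SAP, Statistical Design and Power: "An intent-to-treat approach will be used to estimate the magnitude and statistical significance of intervention effects at immediate post-intervention". Also: "Each outcome will be evaluated in a separate generalized linear mixed model", with the Intervention by Time interaction as the test. The SAP does not define the intent-to-treat set and gives no rule for missing outcomes. It expects 15% attrition and justifies this by the class being required.

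**Means of follow-up.** Under Protocol 5.1 the follow-up surveys are links emailed by university staff. Under 5.6 those staff hold contact details for longitudinal data collection. Under 4.4 payment is per completed follow-up assessment ($20, $25 and $30).

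**The concern.** An intent-to-treat analysis needs outcomes from students who were randomised and then stopped the programme. Staff who follow the visible text have no described way to keep surveying such a student. If surveys end when the curriculum does, the post-baseline outcome is never collected.

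The loss is unlikely to be even between arms. In the fall only the immediate arm has sessions and mentor meetings; the waitlist arm takes the baseline survey and starts the intervention in spring (Protocol 5.1). Before the week 9 assessment, then, dislike of the curriculum can drive loss mainly in the immediate arm, and that dislike may be related to how a student responds. The comparison would tilt towards students who accepted the programme.

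The SAP's reason for expecting modest attrition offers little protection. The class may be required, but 7.2 provides reassignment to another one.

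**Working it through.** **1. The plan's own attrition figure.** From the SAP: 255 recruited, 15% attrition. 255 × (1 − 0.15) = 216.75, which matches the stated analytic sample of 216. Expected losses are 255 × 0.15 = 38.25, about 38 students. The documents do not split these by arm or by reason, so the number lost through rejecting the curriculum cannot be computed. As an outer bound, with 1:1 allocation (assumed, since the ratio is not stated) and every loss in the immediate arm, 38 / 127.5 = 0.298, about 30% of that arm.

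**2. What the mixed model can recover.** A likelihood-based model keeps a leaver's baseline record in the randomised arm. It handles the missing follow-up value without bias if data are missing at random given what the model contains. The basic model in the SAP contains arm, time, their interaction, and classroom and individual effects. The SAP assumes a correlation of r = 0.25 between assessments. A baseline value then explains r² = 0.25² = 0.0625, about 6%, of the variance at follow-up, so it says little about a leaver's unseen outcome.

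**3. Illustration of size.** Assumptions, none from the documents except the 0.20 (the SAP's lower target effect):
- share q of the immediate arm leaves because of the curriculum: 10% or 15%;
- effect in stayers: 0.20 SD;
- effect in leavers: 0 or −0.10 SD;
- waitlist arm intact, and leavers otherwise comparable to stayers, so that the observed-data estimate is 0.20.

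True intent-to-treat effect = (1 − q) × 0.20 + q × (effect in leavers). Overstatement = 0.20 / true effect − 1.

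| q | Effect in leavers | True effect | Overstatement |
|---|---|---|---|
| 10% | 0 | 0.90 × 0.20 + 0.10 × 0 = 0.18 | 0.20/0.18 − 1 = 11% |
| 10% | −0.10 | 0.18 − 0.01 = 0.17 | 0.20/0.17 − 1 = 18% |
| 15% | 0 | 0.85 × 0.20 + 0.15 × 0 = 0.17 | 18% |
| 15% | −0.10 | 0.17 − 0.015 = 0.155 | 0.20/0.155 − 1 = 29% |

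**4. Wider range.** In absolute terms the overstatement is q × Δ, where Δ is how much worse leavers' unseen change is than stayers'. For q from 5% to 15% and Δ from 0.2 to 0.8 SD, it runs from 0.05 × 0.2 = 0.01 to 0.15 × 0.8 = 0.12 SD, against a target of 0.20. The lower end is negligible and the upper end is more than half the target. These figures are for continuous outcomes; they do not carry over directly to the logit scale used for binary ones.

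**The case against.** The strongest reply is that this is a silence and not a rule. Three stronger readings are tempting, and the documents support none of them.

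- *A reader might infer that leaving the class ends research participation.* Section 7.2 runs the other way: a student leaves the research and is then given another class. Nothing says that a class change alone ends the surveys.
- *A reader might infer from n/a in 10.8 that data collection stops.* No reason is given for the entry. The item opens with an if-applicable clause and with withdrawal without the participant's consent, although its second sentence covers withdrawal for any reason. The entry leaves the matter unspecified and forbids nothing.
- *A reader might infer that the analysis will be of completers only and will lose precisely those who reject the curriculum.* Students may be lost for other reasons, emailed links could still reach a student who has changed class, and a mixed model retains baseline records. Departures from missing at random can be examined in sensitivity analyses.

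It is also fair to say that the assent form is not among the documents available and may already offer separate choices, and that the percentages rest on assumed inputs.

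All of that stands. What remains is that every exit after enrolment in the visible text is from the study as a whole, the one question on continued follow-up goes unanswered, and the SAP gives no missing-data rule. Sensitivity analysis can bound the effect of outcomes that were not collected; it cannot supply them.

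**Conclusion.** The concern holds as a gap in the plan. Post-baseline outcomes of students who stop the curriculum **may** be missing from the intent-to-treat analysis, and the SAP does not say on what assumption it would then be valid. Before week 9 the loss can arise mainly in the immediate arm and may relate to response.

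The size is unknown. The 11% to 29% range depends on 10% to 15% of the immediate arm leaving because of the curriculum, a leaver effect of 0 to −0.10 SD, and an intact waitlist arm. It shows what could happen and is not a forecast. The change is worth making because it alters which outcomes are collected, and that cannot be put right after the surveys have closed.

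**What to change.** 1. In Protocol 7.2, 7.3 and 10.8, and in the assent form if it does not already do so, offer two separate voluntary choices: stop the curriculum, or stop the surveys. Keep the right to leave both.
2. Keep sending the same survey links and gift cards, on the same schedule, to students who stop only the curriculum.
3. In the SAP, define the intent-to-treat set as all randomised students analysed in their assigned arm, state the missing-data assumption, and add a sensitivity analysis for departures from it. Report losses by arm and by type of exit.
4. While editing, reconcile where a non-participating student is placed: an elective (4.1), the same class without surveys (5.13), or a class without the curriculum (7.2).

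The cost is protocol and assent wording and slightly more follow-up contact. The surveys are already online, contact details are already held for follow-up, and the follow-up payments are already planned.
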